14.2 Serious Adverse Event (SAE)

An event that is serious must be recorded on the AE CRF and on the CRO SAE Report Form, and requires expeditious handling to comply with regulatory requirements.

An AE or suspected adverse reaction is considered “serious” if, in the opinion of either the investigator or Sponsor, it results in any of the following outcomes:

- Death.
- Life-threatening event.
- Inpatient hospitalization or prolongation of existing hospitalization.
- Persistent or significant incapacity or substantial disruption of the ability to conduct normal life functions.
- Congenital anomaly/birth defect.
- Is an important medical event - defined as a medical event(s) that may not result in death, be life-threatening, or require hospitalization but, based upon appropriate medical judgment, may jeopardize the patient/subject and may require medical or surgical intervention to prevent one of the outcomes listed in the definition above. Examples of such medical events include allergic bronchospasm requiring intensive treatment in an emergency room or at home, blood dyscrasias or convulsions that do not result in inpatient hospitalization, or the development of drug dependency or drug abuse.

Events NOT considered to be SAEs are:

- Hospitalizations for the treatment, which was elective or pre-planned, of a pre-existing condition that did not worsen, and
- Treatment on an emergency, outpatient basis, for an event not fulfilling any of the definitions of “serious” given above and not resulting in hospital admission.

AEs classified as “serious” by either the investigator or the Sponsor require expeditious handling and reporting to CRO to comply with regulatory requirements. **All serious AEs, whether related or unrelated to test article, must be immediately reported by telephone to the Medical Monitor and, in the event that he/she is unavailable, to the Project Manager.** Written notification of all SAEs should be sent to the Project Manager by email or confirmed facsimile transmission. These include those SAEs listed in the protocol or investigator brochure and must include an assessment of whether there is a reasonable possibility that the drug caused the event.

Study endpoints that are SAEs (e.g., all-cause mortality) must be reported in accordance with the protocol unless there is evidence suggesting a causal relationship between the drug and the event (e.g., death from anaphylaxis). In this case, the investigator must immediately report the event to the Sponsor. In addition, such information should also be provided to the site’s respective IRB per their governing guidelines for SAE reporting.

If only limited information is initially available, follow-up reports are required. Should the investigator become aware of an SAE (regardless of its relationship to test article) that occurs within 30 days after stopping the test article, the SAE must be reported in accordance with procedures specified in this protocol. In the event of death, if an autopsy is performed, a copy of the report should be sent to Sponsor, if available.

As required, CRO will notify participating investigators of all suspected adverse reactions that are serious and unexpected. This notification will be in the form of an IND safety report of potential serious risks as soon as possible but no later than 15 calendar days after the Sponsor determines that the information is “reportable” according to the criteria listed in 21 CFR Section 312.32. These are:

- i) Serious and unexpected suspected adverse reactions,
- ii) Findings from other studies including epidemiological studies, pooled analyses, or other clinical studies that suggest a significant risk in humans exposed to the test articles,
- iii) Findings from animal or in vitro tests that suggest a significant risk to humans exposed to the test articles or reports of significant organ toxicity at or near the expected human exposure, and
- iv) Clinically important increases in the rate of occurrence of serious suspected adverse reactions.

Upon receiving such notices, the investigator must review and retain the notice with the Investigator Brochure and immediately submit a copy of this information to the responsible IRB according to local regulations. The investigator and IRB will determine if the informed consent/assent requires revision. The investigator should also comply with the IRB procedures for reporting any other safety information. Where required, submission of safety updates by the investigator to Health Authorities should be handled according to local regulations.

14.3 Pregnancy

WOCBP (see Section 5.1.1 for definition) must have a negative UPT prior to study enrollment and must use a highly effective method of birth control during the course of the study, in a manner such that risk of failure is minimized. Prior to study enrollment, WOCBP must be advised of the importance of avoiding pregnancy during trial participation and the potential risk factors for an unintentional pregnancy. The subject and parent/guardian must sign an informed consent/assent form documenting this discussion.

During the study, all WOCBP should be instructed to contact the investigator immediately if they suspect they might be pregnant (e.g., missed or late menstrual period).

WOCBP enrolling into the study must have a pregnancy test prior to study therapy, and monthly throughout the course of the study. The study therapy must be withheld until the results of laboratory pregnancy testing are known, and a negative UPT must be confirmed to continue in the trial. If pregnancy is confirmed during screening, the subject must not receive test article and must not be enrolled in the study.

If a subject or investigator suspects that a subject may be pregnant at any time during the study, the test article must be withheld until the results of laboratory pregnancy testing are available. If pregnancy is confirmed, the subject must not apply further test article and must be discontinued from the study.

If following initiation of study treatment, it is subsequently discovered that a trial subject was pregnant or may have been pregnant at the time of test article exposure, the investigator must immediately notify the Medical Monitor of this event, and record the pregnancy on the appropriate pregnancy surveillance form. The form will be sent to CRO. The investigator must notify the IRB of any pregnancy associated with the study therapy and keep careful source documentation of the event.

Protocol-required procedures for those subjects that are discontinued from the study must be performed on the subject unless contraindicated by pregnancy (e.g., x-ray studies). Other appropriate pregnancy follow-up procedures should be considered if indicated, including counseling of the subject by the investigator and her managing physician or health care provider (e.g., obstetrician). In addition, the investigator must report to CRO, on the appropriate pregnancy surveillance form(s), any follow-up information regarding the course of the pregnancy, including perinatal and neonatal outcome. Although pregnancy itself is not an AE, any complications during pregnancy should be recorded as AEs (or SAEs, if they fulfill the SAE criteria). Abortion, whether accidental, therapeutic, or spontaneous should be reported as an SAE. Offspring should be followed for a minimum of eight weeks. Any congenital anomaly/birth defect in a child born to a

subject exposed to the test article(s) should be recorded as an SAE and details documented in the pregnancy surveillance form.

15. BLINDING/UNBLINDING

Blinding is important for the integrity of this clinical drug trial. However, the blind may be broken in the event of a medical emergency in a subject, in which knowledge of the test article identity is critical to the subject's management. Before breaking the blind for a subject, the investigator should determine that the information is necessary (i.e., that it will alter the subject's immediate management). In many cases, particularly when the emergency is clearly not test article related, the problem may be effectively managed by assuming that the subject is receiving active product without the need for unblinding. The need to break the blind should first be discussed with the responsible Medical Monitor and the best method to do this will be determined.

16. CLINICAL SUPPLIES

16.1 Test Article Information

Test articles will be packaged and labeled by the Sponsor or designee. Detailed information on the packaging/labeling, blinding/unblinding, storage and preparation, dispensing, accountability etc. is included in Appendix 3.

16.2 Supplies Provided by CRO

- CRFs
- Source document draft templates
- Site regulatory binder or document filing system
- UPT kits
- Weighing scales (if necessary)
- High quality digital camera and any associated software (if needed)

16.3 Supplies Provided by Investigator

- Urine collection containers for UPTs
- Computer to store and view photographs of subjects

17. STATISTICAL CONSIDERATIONS

17.1 Study Endpoints

17.1.1 Efficacy Endpoints

Primary Endpoints (Hierarchical):

- **P1:** Proportion of subjects in each treatment group achieving “success” at Week 12, with “success” defined as an IGA score of “clear (score=0)” or “almost clear (score=1)” AND at least a two-point reduction in IGA compared to Baseline.
- **P2:** Absolute change from Baseline in non-inflammatory lesion counts in each treatment group at Week 12.
- **P3:** Absolute change from Baseline in inflammatory lesion counts in each treatment group at Week 12.

Secondary Endpoints (Hierarchical):

- **S1:** Absolute change from Baseline in total lesion counts (including inflammatory and non-inflammatory) in each treatment group at Week 12.
- **S2:** Percent change from Baseline in total lesion counts (including inflammatory and non-inflammatory) in each treatment group at Week 12.
- **S3:** Percent change from Baseline in non-inflammatory lesions count in each treatment group at Week 12.
- **S4:** Percent change from Baseline in inflammatory lesions count in each treatment group at Week 12.

17.1.2 Safety Endpoints

- Local and systemic AEs at every visit (Baseline, Weeks 4, 8, and 12).
- LSRs: telangiectasia, skin atrophy, striae rubrae, erythema, edema, scaling/dryness, stinging/burning, and pruritus scored by frequency and severity at every visit (Baseline, Weeks 4, 8, and 12).
- UPTs in all WOCBP at every visit (Baseline, Weeks 4, 8, and 12).
- Material changes from Baseline in ECGs at Week 12.

17.2 Sample Size Calculations and Power Considerations

Assumptions used for sample size calculation were estimated from Phase 2 Dose Escalation Study (171-7151-201) [2], using a subset of subjects with 30-75 inflammatory lesions and 30-100 non-inflammatory lesions at Baseline. Sample size calculations were performed on the basis of the formulas for testing superiority in terms of mean differences and odds ratio of Wang and Chow.

All the hypothesis tests for the primary endpoints have to be performed at the same significance level $\alpha=0.05$ two-sided and the failure to reject a null hypothesis will imply the failure of rejecting all of the subsequent null hypotheses.

In order to keep the overall Type II error $\beta=0.1$ for the whole study, the sample size for the three hypothesis tests on the primary endpoints will be calculated considering an individual Type II error $\beta=0.033$.

For an IGA success rate of (continuity corrected) 14.00% for CB-03-01 cream and 2.17% for vehicle cream (odds ratio=7), sample size was estimated to be 202 subjects per treatment group.

For a mean absolute change from Baseline in non-inflammatory lesion counts of -22 for CB-03-01 cream and -1 for vehicle cream (standard deviation=17), sample size was calculated to be 19 subjects per treatment group.

For a mean absolute change from Baseline in inflammatory lesion counts of -14 for CB-03-01 cream and -11 for vehicle cream (standard deviation=17), sample size was calculated to be 334 subjects per treatment group.

The hypothesis test for the secondary endpoints will be performed at the same significance level $\alpha=0.05$ two-sided of the primary endpoints if and only if all the null hypotheses on the primary endpoints are rejected.

For a mean absolute change from Baseline in total lesion counts of -35 for CB-03-01 cream and -13 for vehicle cream (standard deviation=17), sample size was calculated to be 13 subjects per treatment group.

For a mean percent change from Baseline in total lesion counts of -35 for CB-03-01 cream and -14 for vehicle cream (standard deviation=40), sample size was calculated to be 77 subjects per treatment group.

For a mean percent change from Baseline in non-inflammatory lesion counts of -33 for CB-03-01 cream and -5 for vehicle cream (standard deviation=40), sample size was calculated to be 43 subjects per treatment group.

For a mean percent change from Baseline in inflammatory lesion counts of -37 for CB-03-01 cream and -23 for vehicle cream (standard deviation=40), sample size was calculated to be 172 subjects per treatment group.

Based on those assumptions, at least 350 subjects in each treatment group (CB-03-01 cream, 1% BID and vehicle BID) will be included in each Phase 3 study to provide sufficient power (90%) with the chosen primary endpoints.

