	
For a mean absolute change from Baseline in non-inflammatory lesion counts of -22 for CB-03-01 cream and -1 for vehicle cream (standard deviation=17), sample size was calculated to be 19 subjects per treatment group.
 
For a mean absolute change from Baseline in inflammatory lesion counts of -15 for CB-03-01 cream and -10 for vehicle cream (standard deviation=17), sample size was calculated to be 334 subjects per treatment group.
 
The hypothesis test for the secondary endpoints will be performed at the same significance level $\alpha=0.05$ two-sided of the primary endpoints if and only if all the null hypotheses on the primary endpoints are rejected.
 
For a mean absolute change from Baseline in total lesion counts of -35 for CB-03-01 cream and -13 for vehicle cream (standard deviation=17), sample size was calculated to be 13 subjects per treatment group.
 
For a mean percent change from Baseline in total lesion counts of -35 for CB-03-01 cream and -14 for vehicle cream (standard deviation=40), sample size was calculated to be 77 subjects per treatment group.
 
For a mean percent change from Baseline in non-inflammatory lesion counts of -33 for CB-03-01 cream and -5 for vehicle cream (standard deviation=40), sample size was calculated to be 43 subjects per treatment group.
 
For a mean percent change from Baseline in inflammatory lesion counts of -37 for CB-03-01 cream and -23 for vehicle cream (standard deviation=40), sample size was calculated to be 172 subjects per treatment group.
 
Based on those assumptions, at least 350 subjects in each treatment group (CB-03-01 cream, 1% BID and vehicle BID) will be included into each Phase 3 study to provide sufficient power (90%) with the chosen primary endpoints.

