**4.3.2 Absolute change from baseline in NILC in each treatment group at Week 12**

$$N_{\text{TEST}} = N_{\text{VEHICLE}} = \frac{2\sigma^2(z_{\alpha/2} + z_{\beta})^2}{(\mu_{\text{NILC,TEST}} - \mu_{\text{NILC,VEHICLE}})^2}$$

A post-hoc analysis of the data collected in the Phase 2 Dose Escalation Study 171-7151-201 (6) performed only for the subjects with 30-75 inflammatory lesions and 30-100 non-inflammatory lesions at baseline provided the following results for the least square means (i.e. the means obtained after having controlled for the fixed effects and the covariate of the ANCOVA) of the absolute change from baseline in non-inflammatory lesions count and for the related sample size estimation.

	Number of subjects	Least Square Mean
TEST	24	-22.398746
VEHICLE	22	-0.924803

Considering a mean absolute change from baseline in non-inflammatory lesions count of **-22** for TEST treatment group and **-1** for VEHICLE treatment group and a common standard deviation of **17**, we obtain the following estimate of the sample size.

$$\alpha = 0.05 \text{ two - sided}, \beta = 0.033, \mu_{\text{ILC,TEST}} = -22, \mu_{\text{ILC,VEHICLE}} = -1, \sigma = 17$$

$$N_{\text{TEST}} = N_{\text{VEHICLE}} = 19$$

**19 subjects per group** should be enrolled in order to have 19 subjects per group included into the ITT Set.

#### 4.3.3 Absolute change from Baseline in ILC in each treatment group at Week 12

$$N_{\text{TEST}} = N_{\text{VEHICLE}} = \frac{2\sigma^2(z_{\alpha/2} + z_{\beta})^2}{(\mu_{\text{ILC,TEST}} - \mu_{\text{ILC,VEHICLE}})^2}$$

A post-hoc analysis of the data collected in the Phase 2 Dose Escalation Study 171-7151-201 (6) performed only for the subjects with 30-75 inflammatory lesions and 30-100 non-inflammatory lesions at baseline provided the following results for the least square means (i.e. the means obtained after having controlled for the fixed effects and the covariate of the ANCOVA) of the absolute change from baseline in inflammatory lesions count and for the related sample size estimation.

	Number of subjects	Least Square Mean
TEST	24	-14.473098
VEHICLE	22	-10.621723

Considering a mean absolute change from baseline in inflammatory lesions count of **-15** for TEST treatment group and **-10** for VEHICLE treatment group and a common standard deviation of **17**, we obtain the following estimate of the sample size.

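### The sample size for inflammatory lesions (P3), which sets the size of the trial, follows neither from the means in Protocol 17.2 nor from the Phase 2 estimate, and 350 per group gives less than 90% power on either

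*Protocol*

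**What the plan says.** Three places give the planning means for P3, and they do not agree.

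- Protocol 17.2: "inflammatory lesion counts of -14 for CB-03-01 cream and -11 for vehicle cream (standard deviation=17), sample size was calculated to be 334 subjects" per group.
- Protocol Synopsis, sample size row: "inflammatory lesion counts of -15 for CB-03-01 cream and -10 for vehicle cream (standard deviation=17), sample size was calculated to be 334 subjects" per group.
- SAP 4.3.3: "inflammatory lesions count of -15 for TEST treatment group and -10 for VEHICLE treatment group", with SD 17 and 334 per group.

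The SD and the sample size are the same in all three; only the means differ. SAP 4.3.3 also prints the Phase 2 least-squares means from which the planning values are drawn: -14.473098 (24 subjects on active) and -10.621723 (22 on vehicle). Protocol 17.2 and SAP 4.3 both say the assumptions were estimated from that Phase 2 study. SAP 1.1 reports no change from the protocol.

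Each primary test is two-sided at 0.05 with an individual Type II error of 0.033, chosen to hold the overall Type II error at 0.1. The three primary requirements are 202 (P1), 19 (P2) and 334 (P3) per group. Protocol 17.2 concludes that, on its listed assumptions, at least 350 per group are enough "to provide sufficient power (90%) with the chosen primary endpoints". SAP 4.2 requires all three primary nulls to be rejected before superiority is claimed.

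**The concern.** A sample size of 334 cannot follow from both a difference of 3 and a difference of 5 at the same SD, alpha and beta. At least one statement is therefore wrong as written, and it concerns the endpoint that sets the size of the trial.

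The difference of 5 is also not what Phase 2 showed. Rounding -14.473 and -10.622 to the nearest integers gives the -14 and -11 of Protocol 17.2. The -15 and -10 move both means outward, which widens the difference from 3.85 to 5. No reason is given, and none of the other five lesion endpoints was treated this way.

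The stake is the power claim. Because P1, P2 and P3 must all succeed, overall power can be no higher than P3 power. If the planning difference is really 3 or 3.85, the 90% printed in both documents is not met.

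**Working it through.** **Inputs.** Two-sided alpha 0.05 and beta 0.033 (Protocol 17.2, SAP 4.3); SD 17 (all three places); 1:1 allocation; 350 per group planned; 732 enrolled (SAP 2.4), taken as 366 per group. Differences: 5 (Synopsis, SAP 4.3.3); 3 (Protocol 17.2); 14.473098 - 10.621723 = 3.851 (Phase 2, SAP 4.3.3).

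**Formula (SAP 4.3.3).** N per group = 2 × SD² × (z for alpha/2 + z for beta)² / d².

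Here (1.95996 + 1.8384)² = 14.428 and 2 × 17² = 578.

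**Reproducing the plan.** For d = 5, 578 × 14.428 / 25 = 333.6, so 334. The same formula returns 19 for P2 and, with beta 0.1, the secondary figures 13, 77, 43 and 172. The SAP's odds-ratio formula gives 201.3 for P1, so 202. The formula is therefore the one the plan used, and only the P3 means in Protocol 17.2 fail to give their stated N.

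**The other two differences.**
- d = 3: 578 × 14.428 / 9 = 926.6, so 927.
- d = 3.851: 578 × 14.428 / 14.833 = 562.2, so 563.

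**Power.** P3 power = Phi(d / (17 × √(2/n)) - 1.96). At n = 350 the standard error is 17 × 0.07559 = 1.2851.
- d = 5: Phi(3.891 - 1.960) = 97.3%
- d = 3.851: Phi(2.997 - 1.960) = 85.0%
- d = 3: Phi(2.334 - 1.960) = 64.6%

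| Difference | N per group at beta 0.033 | P3 power, 350 per group | P3 power, 366 per group | Product of P1-P3 power, 350 per group |
|---|---|---|---|---|
| 5 | 334 | 97.3% | 97.8% | 97.2% |
| 3.85 | 563 | 85.0% | 86.5% | 84.9% |
| 3 | 927 | 64.6% | 66.5% | 64.5% |

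At 350 per group P1 power is 99.9% and P2 power is about 100%, so P3 alone determines the last column and the correlation between endpoints hardly matters. Even if P3 were allowed the whole 10% Type II error, it would need 410 per group for a difference of 3.85 and 675 for a difference of 3.

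**Planning difference against the Phase 2 difference (SAP 4.3.2 to 4.3.7).**

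| Endpoint | Phase 2 | Planned |
|---|---|---|
| Non-inflammatory, absolute (P2) | 21.47 | 21 |
| Inflammatory, absolute (P3) | 3.85 | 5 |
| Total, absolute (S1) | 22.65 | 22 |
| Total, percent (S2) | 21.31 | 21 |
| Non-inflammatory, percent (S3) | 28.59 | 28 |
| Inflammatory, percent (S4) | 14.21 | 14 |

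P3 is the only one enlarged: 5 / 3.851 = 1.30.

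**Sensitivity to the SD.** The SAP gives no Phase 2 SD, so 17 is an assumption in the 3.85 row. At 350 per group and d = 3.85, P3 power is about 92% at SD 15, 85% at SD 17 and 76% at SD 19. Reaching 90% needs an SD of about 15.7 or less; for d = 3 it needs about 12.2 or less.

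**The case against.** The best defence is that 334 is correct where it is actually derived. SAP 4.3.3 sets out formula, inputs and result; the Synopsis agrees; and on those inputs 350 per group gives about 97% power, well above 90%. On this view -14 and -11 in Protocol 17.2 are rounded figures placed beside an N computed elsewhere. The same section also shortens the odds ratio to 7, against 7.3 in the Synopsis and 7.3256 in the SAP, and keeps 202. That reading is plausible, and nothing shows that anyone meant to design for a difference of 3. The 64.6% is best read as what Protocol 17.2 implies as written.

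A second argument is that 3.85 is too imprecise to serve as a benchmark. With 24 and 22 subjects and SD 17 its standard error is 17 × √(1/24 + 1/22) = 5.0, giving a 95% interval of about -6 to 14, so 5 is well within the data. A sponsor may plan on such a value, and the SAP prints the Phase 2 means directly above it. This stands as far as it goes. It does not support describing 5 as estimated from Phase 2 when the printed estimate is 3.85, and imprecision is no reason to round in the favourable direction for one endpoint only.

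Third, the 85% depends on SD 17, which is not shown to be a Phase 2 value. That is right, and the conclusion for 3.85 would change at an SD of about 15.7 or less. However, 17 is the only SD that either document gives for P3.

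One coincidence should be set aside. A one-sided 0.05 test with 90% power and a difference of 3.85 also gives 334. Both documents specify two-sided 0.05 and beta 0.033, and the SAP derives 334 explicitly from -15 and -10.

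**Conclusion.** The point holds. Protocol 17.2 is wrong as written: its P3 inputs require 927 per group, not 334, and on them 350 per group gives 64.6% power rather than 90%. The figure 334 is arithmetically right only for a difference of 5, which is 30% above the Phase 2 estimate it is attributed to. At the Phase 2 difference of 3.85, P3 power is 85.0% at 350 per group and 86.5% at 366, and overall power is about 85% at 350. Both are also below the 96.7% that beta 0.033 promises for P3. The 90% claim is met, at about 97% overall, only if the true difference is 5.

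These figures assume SD 17, two-sided 0.05 and no loss of information from missing data. SAP 4.3 mentions an allowance for non-completers, but no dropout rate is given and none was applied; any loss would lower the powers.

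**What to change.** Keep the sample size, and change the text as follows.

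- Make the P3 means in Protocol 17.2 agree with the Synopsis and SAP 4.3.3, so that the inputs printed beside 334 produce 334. If the protocol is no longer open to amendment, record the correction in SAP 1.1.
- In all three places, say that -15 versus -10 is a design assumption larger than the Phase 2 least-squares difference of 3.85, give the reason for choosing it, and state where the SD of 17 comes from.
- Replace the unqualified 90% with conditional statements. Suggested text: with SD 17, 350 subjects per group give about 97% power for P3 at a difference of 5 and about 85% at the Phase 2 difference of 3.85; overall power for P1 to P3 is limited by P3. Add the SD range (about 92% at SD 15 and 76% at SD 19, for a difference of 3.85).

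The cost is edits to wording and figures in Protocol 17.2, the Synopsis and SAP 4.3 and 4.3.3. No patients are added, and the analysis, testing order and Type I error are untouched. The stated power becomes less favourable.
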